Washington) will be used to assess home ambulatory function. Previous research by our group has validated this device for patients with PD and has shown that step count as measured by this device is highly correlated with disease severity in PD (85). Subjects will wear the SAM at home over 48 hours while performing their usual daily routines (removing it during bathing and sleep). Recording will be done on the days that immediately precede or follow the on-site clinical testing of the other outcome measures. Placement of the SAM will be taught to the subject on site during their first testing session. Individual calibration will be done based on each subject's height and gait (e.g. subjects will perform a 30-foot walk while an examiner records time and number of steps without the SAM). Two variables will be measured: mean step count per day and maximal number of steps per hour.

Statistical Analysis Plan (SAP):

The data from the study will be entered into a dataset and validated by the investigators. Descriptive statistics will be calculated for all variables using SAS version 9.1 (SAS institute, Cary, N.C.). Exploratory data analyzes will be performed to check the data for extreme values and to test for normality (Kolmogorov-Smirnov test). If our data is not normally distributed, we will try conventional normalizing and/or variance stabilizing transformations to obtain something close enough to a Gaussian distribution to enable the use of parametric statistics. A two-tailed $p < 0.05$ will be considered indicative of a significant result. Below is a description of the statistical analyses to test each hypothesis of this study:

Hypothesis I: The combined intervention TAEX + TCOG group will show greater improvement in EF than either group alone.

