Our dependent variables on DT performance are: 1) the number of words generated per second, 2) spatiotemporal gait parameters including walking speed, stride length, cycle time, and variability of cycle time, 3) Cognitive Cost and 4) Gait Cost. Each dependent variable will be evaluated with a parametric Mixed Models Repeated Measures Analysis of Variance (ANOVA), with Group as the between factor (TAEX, TCOG, TAEX+TCOG) and Time as the within factor (pre-test, post-test). Therefore, each intervention group will be compared against each other, and against the delayed entry phase. Similar to the analysis described under Hypothesis I, we will adjust for potential confounding variables, run a Tukey's Honestly Significant Difference post-hoc test, and perform an intention-to-treat analysis for Hypothesis II.

Hypothesis III: Improvement in DT performance will be associated with improvement in IADLs function.

Our IADL measures are: 1) OARS IADLs, 2) Timed IADLs and 3) daily activity as measured by the SAM. To test Hypothesis III, these measures will be converted into change scores. Therefore our dependent measures are: 1) OARS change scores (post-test – pretest), 2) Timed IADLs (post-test – pretest), 3) SAM change scores (post-test – pretest). These measures will be correlated with DT performance measures, also represented as change scores.

Correlations between OARS IADLs change scores and DT change scores will be calculated using non-parametric statistics, Spearman Correlation Analysis, because OARS produces rank-ordered data. Correlations between Timed IADLs change and DT change, as well as correlations between SAM change and DT change will be calculated using parametric statistics: Pearson Product Moment Correlation Analysis.

Secondary analyses:

In order to investigate whether EF improvements are associated with cardiopulmonary fitness improvements, we will run Pearson Product Moment Correlations. Correlated variables will be: 1) change in EF performance (z-scores and ICE) where change is calculated as pre-test – post-test, and 2) change in cardiopulmonary fitness measures (Peak VO₂ max, METs, 6 min walk test time) where change is calculated as pre-test – post-test.

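### The change-score correlations for Hypothesis III and for EF versus fitness name no Group adjustment, so arm differences could create or dilute an association

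*Combined protocol and SAP*

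**What the plan says.** Hypothesis III reads "Improvement in DT performance will be associated with improvement in IADLs function". The SAP turns OARS IADL, Timed IADL and step-monitor (SAM) results into post-minus-pre changes and states "These measures will be correlated with DT performance measures, also represented as change scores". The methods are simple ones. For OARS, "Correlations between OARS IADLs change scores and DT change scores will be calculated using non-parametric statistics, Spearman Correlation Analysis". Timed IADL is handled by Pearson, "as well as correlations between SAM change and DT change will be calculated using parametric statistics: Pearson Product Moment Correlation Analysis". Under Secondary analyses, for EF change against change in peak VO2, METs and six-minute walk, "we will run Pearson Product Moment Correlations".

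None of these sentences mentions Group, a partial correlation or separate analyses by arm. Group appears as a factor only in the ANOVAs for Hypotheses I and II. Covariate adjustment is described under Hypothesis I and carried over by name to Hypothesis II only.

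The same SAP predicts that the arms will differ. Hypothesis I is "The combined intervention TAEX + TCOG group will show greater improvement in EF than either group alone", and Hypothesis II says the same of DT. The intervention section gives treadmill exercise to the TAEX and combined arms but not to TCOG.

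**The concern.** Aim 3 asks whether a gain in DT carries over into everyday function, which is most naturally a question about patients: do those who gain more on DT also gain more on IADLs? The EF–fitness analysis asks the same kind of question. Group can be a common cause of both changes. If one programme moves both measures, patients from that arm sit high on both axes and a pooled correlation appears even when, inside every arm, the two changes are unrelated. If the programmes move different measures, the arm means pull against a real within-arm link and weaken it. In either case a p-value from the pooled coefficient mixes a patient-level link with a comparison of programmes, and a reader could take one for the other.

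**Working it through.** **Inputs from the documents.** Three arms; treadmill training in two of them; a two-tailed p below 0.05 "will be considered indicative of a significant result" (SAP, opening paragraph). The documents give no sample size, SD, arm difference or expected correlation, so there is no figure of the plan's own to reproduce.

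**Assumptions.** Equal arms, mostly 20–40 patients each; both changes scored so that positive means improvement; within-arm SD of 1 for each change; arm shifts of 0.5 to 1.0 within-arm SD.

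**Formula.** Let ρw be the within-arm correlation, Bxx and Byy the variances of the arm means, and Bxy their covariance. Then

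ρ(pooled) = (ρw + Bxy) / √[(1 + Bxx)(1 + Byy)].

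**1. Arms differ on both variables, ρw = 0.** With the combined arm ahead by d on both, Bxx = Byy = Bxy = d²/3 − (d/3)² = 2d²/9. Rejection rates are from simulation of the pooled test (N − 2 degrees of freedom).

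| d (SD) | Pooled ρ | Rejection, pooled test |
|---|---|---|
| 0.5 | 0.0556/1.0556 = 0.053 | 7–9% |
| 0.8 | 0.1422/1.1422 = 0.125 | 13%, 19%, 28% at 15, 25, 40 per arm |
| 1.0 | 0.2222/1.2222 = 0.182 | 28%, 41%, 52–53% at 20, 30, 40 per arm |

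With arm means spread 0, 0.5 and 1.0 on both, B = 1.25/3 − 0.25 = 0.167 and ρ = 0.167/1.167 = 0.143, with about 20–35% rejection. Under the same model pooled Spearman behaves almost alike (28–51% at 1.0 SD), so ranking does not protect the OARS analysis. The Group-adjusted test (N − 4 degrees of freedom) rejected about 5% of the time in every case.

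**2. Arms differ on one variable only.** Then Bxy = 0. With ρw = 0 the pooled ρ is 0, so nothing spurious arises. With ρw = 0.30 and a 1.0 SD shift of one arm on one variable, ρ = 0.30/√1.222 = 0.271, a mild dilution.

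**3. EF against fitness, ρw = 0.** Take fitness means of 1/0/1 (TAEX/TCOG/combined) and EF means of a/b/1, with a and b between 0 and 1, so that the combined arm is never behind on EF. Then Bxy = (a + 1)/3 − (2/3)(a + b + 1)/3 = (a + 1 − 2b)/9.
- a = 0, b = 1: Bxy = −1/9, and ρ = −0.111/1.222 = −0.09.
- a = 0.5, b = 0: Bxy = 1/6, and ρ = 0.167/√(1.222 × 1.167) = 0.14.
- a = 1, b = 0: Bxy = 2/9, and ρ = 0.222/1.222 = 0.18.

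**4. Opposing pattern, ρw = 0.30.** Suppose exercise moves fitness (d/0/d) and cognitive training moves EF (0/d/d). Then Bxy = d²/3 − 4d²/9 = −d²/9, and ρ = (0.30 − d²/9)/(1 + 2d²/9).
- d = 0.5: 0.258.
- d = 0.8: 0.200.
- d = 1.0: 0.155.

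At 25 per arm the adjusted test has about 74% power. The pooled test has about 40% at d = 0.8 and 25% at d = 1.0. At d = 0.5, a pattern with the same pooled ρ (TAEX alone moving one variable and TCOG alone the other) gave about 62%.

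**The case against.** The strongest reply has five parts.

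- **Pooling is inferred.** A reader might take the plan to state that all arms are combined. It does not; it is silent. This stands, but one undivided set of correlations is the natural reading, and if another was meant the SAP needs to say so.
- **Only half the mechanism is predicted for Hypothesis III.** A reader might infer that the plan expects arms to differ on both DT and IADLs. It predicts a DT difference, but no hypothesis predicts one in OARS, Timed IADL or SAM. As step 2 shows, a DT difference alone dilutes a true correlation and does not create a false one. This stands, although arm differences in IADLs would follow if DT gains do carry over as Aim 3 supposes.
- **Fitness change is not simply a label for arm.** That reading is tempting because TCOG does no treadmill work. With two of three arms shifted by d, arm explains (2d²/9)/(1 + 2d²/9) of the variance: 5% at 0.5 SD, 18% at 1.0 SD, 33% at 1.5 SD. Reaching half needs d = √4.5, about 2.1 SD, and nothing in the documents supports that.
- **Hypothesis III says only that the changes are associated.** A pooled coefficient does test marginal association, and adjusting for Group removes gain brought about by treatment, which may be part of what carrying over means. So it is too strong to say that the pooled p-value tests nothing relevant. The rejection rates above are false positives for a within-arm link, not for association of any kind.
- **The high rates need large shifts.** No document figure supports a 1 SD lead over two other active arms on both measures, and the OARS section itself warns of a floor effect. The EF–fitness analysis is also secondary, with no formal hypothesis.

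These points limit the size and wording of the concern. They do not supply the missing specification.

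**Conclusion.** The point holds as a gap that should be closed. As written, the correlations for Hypothesis III and for EF against fitness have no Group term, in a plan that predicts arm differences in EF and DT and trains only two of three arms on the treadmill. The effect is possible, not certain. It is minor at shifts of 0.5 SD or less and material from about 0.8 SD. For EF against fitness, the spurious correlation runs from about −0.09 to +0.18 for shifts up to 1 SD, provided the combined arm does at least as well on EF as either single arm. All sizes rest on assumed arm sizes and shifts, equal within-arm SDs, and a reading of the question as one about patients within arms. That arm differences will distort these results cannot be concluded from the documents.

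**What to change.** State in the SAP that the inferential analyses for Hypothesis III and for EF against fitness are adjusted for Group:

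- **Timed IADL, SAM and EF–fitness:** partial Pearson correlation given Group, or regression of one change on the other plus Group.
- **OARS:** partial Spearman given Group, or the same regression on ranks. An unranked regression is not equivalent here.
- **Common slope:** check slope-by-Group, since the adjusted coefficient assumes one slope across arms.
- **Pooled and by-arm correlations:** report as descriptive. Part of the pooled association may run through treatment and is worth showing, but it cannot alone establish a patient-level link.

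The cost is a few sentences and two degrees of freedom (N − 2 becomes N − 4). Group is already recorded, so no new data are needed. With a true within-arm correlation of 0.30, the adjusted analysis recovers about 0.30, with power of roughly 51%, 74% and 92% at 15, 25 and 40 per arm.

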The NAART provides an estimate of intelligence by assessing the ability to read 61 non-phonetic words (70).

Action Fluency:

Action Fluency is a measure of executive function in which the examinee is asked to spontaneously produce as many action words (i.e., verbs) as possible in one minute (71). Previous research has found this test to be particularly sensitive to cognitive decline in patients with PD (72). The total score is the number of different verbs produced in one minute.

Cardiorespiratory Function Measures:

a. Cardiorespiratory fitness test:

A cardiorespiratory fitness test with open circuit spirometry will be conducted in all study subjects (54, 65, 73). For detailed description see section 1.4.7. Data will be expressed as VO_2 in ml/kg/min to account for variation in body weight. Peak ambulatory work load capacity (METs) will also be estimated from exercise tests, as previously reported (54, 73). This test will be conducted in the VAMC Exercise Physiology Lab using non-rebreather masks (Hans Rudolph), velocity-calibrated treadmills and SensorMedics Metabolic Systems (54, 64, 73).

b. Six-minute walking test:

The six-minute walking test will be used as an additional measure of cardiopulmonary performance and gait performance. This test was originally developed for patients with pulmonary disease but has also been used in neurologic populations including stroke (74) and PD (75). The test consists of walking on a track for 6 minutes at a comfortable walking speed. The distance covered in 6 minutes is the outcome measure.

c. Submaximal Effort Treadmill Economy of Gait: Economy of gait is measured using open circuit spirometry during two standard constant load submaximal effort treadmill walking tasks at pre-established gait velocities (1mph and 2mph). The mean rate of VO_2 is calculated based on the final 2.5 minutes of both 5-minute walks under steady state oxygen consumption conditions, as previously described. Patients not achieving a plateau in VO_2 are re-tested at a lower velocity on a different date to eliminate potential confounding effects of fatigue on testing. These tests will be performed on the same day, in order to prevent fatigue becoming an issue, between each 5 minute test, the participant will have a 10 minute rest period.

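### The secondary analysis names six-minute walk time as a fitness variable, but the protocol fixes that time and makes distance the outcome; read literally, the change is zero for everyone who completes both walks

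*Combined protocol and SAP*

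**What the plan says.** The SAP, under Secondary analyses, asks whether EF gains go with gains in cardiopulmonary fitness. The method is stated as "we will run Pearson Product Moment Correlations". One side of each correlation is change in EF (the z-scores and the ICE). The other is change in a fitness measure: peak VO₂, then "METs, 6 min walk test time". Both changes take the same direction, "where change is calculated as pre-test – post-test".

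The protocol describes the walk under Cardiorespiratory Function Measures, item b. Its role is given as follows: "The six-minute walking test will be used as an additional measure of cardiopulmonary performance and gait performance". Its conduct is fixed: "The test consists of walking on a track for 6 minutes at a comfortable walking speed". Its result is named: "The distance covered in 6 minutes is the outcome measure".

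Item d of the same section, Over-ground Gait Economy, describes another walk of the same length. It is done with a portable metabolic monitor on a 100-foot course, and subjects are also told to go as far as they can. Neither item defines a time outcome, provides for recording a stopping time, or says how an incomplete walk is scored.

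**The concern.** A timed walk gives either the time over a set distance or the distance in a set time. This test is the second kind, so its duration is a design constant and carries no information about fitness in anyone who finishes. The SAP sentence nevertheless names time as the variable, and it is the only SAP sentence that specifies the variable for this analysis.

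An analyst who follows the text would have no usable six-minute-walk correlation for any EF domain score or for the ICE. An analyst who uses distance would get a sensible result but would depart from the written plan. Either way, the plan and the report would not match on this item.

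**Working it through.** The documents give no sample size, standard deviation or expected correlation for this analysis, so there is no planned figure to reproduce. The check uses the definition of the statistic.

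**Inputs from the documents**
- Walk duration: 6 minutes (six-minute walking test, item b).
- Outcome of the test: distance (same item).
- Variable to be correlated: time (SAP, Secondary analyses).
- Change: pre-test minus post-test, for both EF and fitness (same section).
- Statistic: Pearson correlation (same section).

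The two-tailed 0.05 threshold plays no part in the check.

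**Step 1. Everyone completes both walks.** Let X be the change in time and Y the change in EF.
- X = 6 − 6 = 0 for each subject, so Var(X) = 0 and cov(X, Y) = 0.
- r = cov(X, Y) / (SD_X × SD_Y) = 0 / (0 × SD_Y) = 0/0, which is undefined.

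A numerical run with an assumed n of 60 gave a variance of 0.0 and no value for r. The choice of n does not matter here.

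**Step 2. Some subjects stop early.** The covariance can be written as (1/n) Σ xᵢ(yᵢ − ȳ). Every subject with xᵢ = 0 drops out of the sum, so the numerator comes only from subjects whose walking time differed between the two tests. Illustration, assuming n = 60 and non-zero changes drawn between −3 and +3 minutes, unrelated to EF:

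| Subjects with non-zero change | Variance of X | r in one draw |
|---|---|---|
| 1 of 60 | 0.143 | −0.06 |
| 3 of 60 | 0.104 | 0.13 |
| 6 of 60 | 0.347 | −0.08 |

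These are single random draws. They show only that r becomes computable; the values mean nothing for the trial.

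**Step 3. Distance in place of time.** Distance varies between subjects, so its change has positive variance and r is defined. With assumed true correlations of 0.30 and 0.50 and 200,000 simulated pairs, r was 0.2999 and 0.5001.

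**Step 4. Direction and unit.**
- Taking both changes as post minus pre gave the same values as pre minus post, because (−1) × (−1) = 1.
- Changing the unit multiplies distance by a positive constant a, and r(aX, Y) = a·cov(X, Y) / (a·SD_X × SD_Y) = r(X, Y).

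**The case against.** The strongest reply is that the protocol largely settles the matter. Distance is the only outcome it defines for this test, so the natural reading of the SAP phrase is a loose label for the six-minute walk result. Distance is the stated outcome at both assessments, so nothing is lost from the data. The SAP also plans descriptive statistics for all variables, and a column of identical values would be noticed before any correlation was reported. The item is secondary, and the protocol calls the walk an additional measure.

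Most of this stands, and it limits the consequence. It does not make the sentence right: the SAP should name the variable that will be analysed, and here it names a different one.

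A reader might infer more than the documents support:
- **Time is constant for everyone, so every six-minute-walk correlation is undefined.** This holds only if every subject completes both walks. The documents do not say that all will, and they give no rule for a walk cut short.
- **One of the three fitness measures is lost.** It is lost only if the team actually tabulates time. Distance remains available.
- **The pre-minus-post direction is a further error, because Hypothesis III uses post minus pre.** Within this analysis both variables use the same direction, so r is unchanged.

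**Conclusion.** The inconsistency is real. It lies in an operative SAP sentence, and both conflicting statements are current text. Taken literally, the planned correlation is undefined if all subjects complete both walks, and otherwise rests on early stopping. This applies to each EF domain score and to the ICE; the number of EF domains is not given, so the affected correlations cannot be counted.

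The reach is one of three fitness variables in one secondary analysis. The peak VO₂ and METs correlations, Hypotheses I to III and their endpoints are untouched. The conclusion rests on the fixed six-minute duration and on the definition of the Pearson coefficient. The n of 60, the early-stopping counts and the correlations of 0.30 and 0.50 are illustrative assumptions, and the conclusion does not depend on them. That time is a slip for distance is the likeliest explanation, but it is an inference, since the documents do not say so.

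**What to change.** In the SAP, Secondary analyses, replace the six-minute walk time entry with: *distance covered in the six-minute walking test (the comfortable-speed track walk described under Cardiorespiratory Function Measures, item b)*. Naming the walk matters because item d describes a second one with a different pacing instruction. Use whatever unit is recorded; the protocol gives none, and r does not depend on it.

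It would help to add, in the same edit, one sentence on how an incomplete walk is scored in this analysis.

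The cost is one phrase, plus that optional sentence. No new data, visits or changes to other analyses are needed.
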